7.11. Study Days 3, and 6 (Study Drug Administration)

All assessments should occur ± 1 day from the scheduled Study Day.

7.11.1. Pre-dose

On Days 3, and 6 the following dosing guideline should be observed prior to dose administration:

- At Investigator discretion, dosing can be HELD or STOPPED at any time for safety reasons or if the patient deteriorates and can longer be administered drug.

The following should be obtained prior to dosing.

- Physical examination
- Vital signs
- Spirometry
- SARS- CoV-2 infection symptom score
- Ordinal Scale for Clinical Improvement assessment
- Adverse event assessment
- Concomitant medication assessment

7.11.2. Days 3 and 6 (Study Drug Administration)

Dosing

PUL-042 administration must be supervised by a health care professional. PUL-042 will be administered via a PARI Sprint nebulizer equiped with a filter valve to prevent aerosol generation. A nose clip will be used during the nebulization procedure. All doses will be administered as a constant volume (4 mL) via nebulization; the nebulizer will be operated until all drug has been delivered. All of the following time points are defined relative to the completion of dosing (T_0).

Note: Missed doses should not be replaced

Post-Dose Guidelines

In previous studies with healthy volunteers, some subjects have demonstrated a transient decrease in lung function, usually asymptomatic. To date, subjects have recovered to at or near baseline lung function values without the administration of rescue medication. However, if after administration of PUL-042 Inhalation Solution there are clinical symptoms of decreased lung function, albuterol (salbutamol) can be administered.

Following dosing, if a reduction of FEV1 $>10\%$ relative to pre-treatment is recorded, the patient should have the FEV1 measurement repeated as clinically indicated. If a reduction of FEV1 $>12\%$ relative to pre-treatment is recorded at 4 hours, the patient must be reviewed by the Principal Investigator prior to further dosing. If a reduction of FEV1 $>12\%$ persists for up to 4 hours and is associated with clinical symptoms over this period, no further investigational treatment should be administered. Albuterol (salbutamol) may be given to symptomatic patients at the discretion of the investigator.

If a reduction of FEV1 >20% relative to pre-treatment is recorded, no further investigational treatment should be administered to that patient. Patients whose COVID-19 condition deteriorates such that they can no longer be given treatment by nebulization or require mechanical ventilation will be discontinued from further dosing.

7.11.3. Days 3 and 6 (T₀ +30 minutes [\pm 15 minutes])

- Vital signs
- Spirometry
- Adverse event assessment
- Concomitant medication assessment

7.12. Study Day 10

Assessments should occur \pm 1 day of target Study Day.

The following assessments will be conducted:

- Physical examination
- Vital signs
- SARS- CoV-2 infection symptom score
- Ordinal Scale for Clinical Improvement assessment
- Adverse event assessment
- Concomitant medication assessment

7.13. Study Day 15

Assessments should occur within +1 day of target Study Day.

The following assessments will be conducted:

- Physical examination
- Vital signs
- SARS- CoV-2 infection symptom score
- Ordinal Scale for Clinical Improvement assessment
- Adverse event assessment
- Concomitant medication assessment

7.14. Early Discontinuation from Dosing and Study Withdrawal

Subjects who have received at least one dose of investigational treatment and are discontinued from dosing should continue to the final assessment at Day 29 according to the schedule of events specified for pre-dose assessments. There will be no post-dose assessments for these subjects.

Should the subject's study participation end prior to the completion of Study Day 15, the following assessments will be conducted as soon as possible after the decision to withdraw from the study is made.

- Serum pregnancy test or urine test (if urine positive, a serum test must be conducted)
- Physical examination
- Vital signs
- Nasopharyngeal or oropharyngeal sample for SARS-CoV-2 testing
- SARS- CoV-2 infection symptom score
- Ordinal Scale for Clinical Improvement assessment
- Adverse event assessment
- Concomitant medication assessment

7.15. Study End (Day 29)

Assessments should occur within +2 days of target Study Day.

Subjects should be followed to Day 29 (28 days post-initial dose of study drug).

- Women who can become pregnant will take a urine pregnancy test. If the test is positive, the results will be confirmed with a blood pregnancy test.
- Nasopharyngeal or oropharyngeal sample for SARS-CoV-2 testing
- SARS- CoV-2 infection symptom score
- Ordinal Scale for Clinical Improvement assessment
- Adverse event assessment
- Concomitant medication assessment

8. CLINICAL EVALUATIONS AND PROCEDURES

8.1. Medical History

Medical history will include significant medical conditions, surgical history, and all medications, both prescription and nonprescription, taken within 14 days prior to screening. Exposure to SARS-CoV-2 will be documented as well as documentation of a positive test for SARS-CoV-2.

8.2. SARS-CoV-2 Infection Assessment

Ordinal Scale for Clinical Improvement: A nine point scale will be used to assess the severity of COVID-19 which has been derived from the draft scale proposed by WHO.⁹

The following table will be used to assess symptoms due to SARS-CoV-2 infection:

Table 2: SARS-CoV-2 Infection Symptom Score

Symptom	Score (0-3)
Cough	
Shortness of breath or difficulty breathing	
Muscle aches or fatigue	
	Score (0-4)
Fever	

Symptom Scores (Cough, Shortness of breath or difficulty breathing, Muscle aches or fatigue)

- 0- None
- 1- Mild (occasional or not bothersome)
- 2- Moderate (frequent or bothersome)
- 3- Severe (interferes with daily activities)

Note: Fever will be scored based on temperature recorded as part of vital signs and graded according to the Toxicity Grading Scale for Healthy Adult and Adolescent Volunteers Enrolled in Preventative Vaccine Clinical Trials:

- 0 No Fever
- 1 - Mild 38.0-38.4°C/100.4-101.1°F
- 2- Moderate 38.5-38.9°C/101.2-102.0°F
- 3-Severe 39.0-40.0°C/102.1-104.0°F
- 4-Life Threatening > 40.0°C/>104.0°F

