7.7. Schedule of Study Activities

The schedule of events is presented in [Table 1](#).

Table 1: Schedule of Events

Event	Screening	Dose 1 ^{a,b}	Dose 2, 3 ^a	Follow-up	Follow-up/Early Discontinuation from Study	Study End
	V1	V2	V3, 4	V5	V6	V7
	Day -2 to Day 1	Day 1 ^b	Days 3, 6	Day 10	Day 15	Day 29
Informed consent	X					
Medical history	X					
Pregnancy test ^c	X				X	X
Physical exam	X	X	X	X	X	
Vital signs ^d	X	X	X	X	X	
Pulse oximetry	X					
Spirometry ^e	X	X	X			
Symptom Score	X	X	X	X	X	X
SARS-CoV-2 test ^f	X				X	X
Ordinal Scale for Clinical Improvement	X	X	X	X	X	X
Study drug administration ^g		X	X			
Adverse events	X	X	X	X	X	X
Concomitant medications	X	X	X	X	X	X
Randomization	X					

^a Vital signs, adverse events, and concomitant medications will be assessed prior to administration of study medication and also at 30 minutes post-dose.

^b There is no Day 0 in this study

^c Urine pregnancy test or serum pregnancy test if women are of child-bearing potential. If urine pregnancy test is positive, a serum pregnancy test must be done. Pregnancy test will be repeated at Day 29 or Early Discontinuation

^d Vital signs will include body temperature, blood pressure measurements, heart rate, and respiratory rate

^e Spirometry will be done at screening to document eligibility. On days of dosing, spirometry will be done pre-dose and at 30 minutes (± 15) minutes post-dose. If the FEV1 is reduced $> 10\%$ compared to the pre-dose baseline the FEV1 should be repeated as clinically indicated

^f SARS-CoV-2 testing will be performed at screening to confirm eligibility if a positive test SARS-CoV-2 has not been documented. SARS-CoV-2 testing will be performed at Early Discontinuation visit

^g Study drug administration must be done by a health care professional

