8.3. Physical Examination and Vital Signs

A qualified medical person will perform a physical examination at all indicated visits.

- Physical examination: general appearance, head, eyes, ears, nose, throat, neck, cardiovascular, lungs, abdomen, lymph nodes, extremities, neurological, skin, musculoskeletal, and other.
- Vital signs will include body temperature, blood pressure, heart rate, and respiratory rate.

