The respiratory symptom score will be calculated by summing the symptom scores from Cough and Shortness of breath or difficulty breathing. The scores from each symptom together with calculated respiratory symptom scores will be summarized by presenting the number and percentage of subjects for each category by visit and treatment group.

The time to the first occurrence of resolution of symptoms defined as the time from the first symptom score of ≥ 1 to a symptom score of 0 will be estimated using the KM method. If a subject had a symptom score of 0 from Baseline through Day 29, then that subject will be excluded from the analysis.

Time to Resolution of Symptoms (days) = (Date of the first symptom score of 0 since the initial score of ≥ 1) - (Date of the initial symptom score of ≥ 1 at or after Baseline) + 1

For each individual symptom and the respiratory symptoms (cough, shortness of breath and difficulty breathing), the KM estimates along with 95% CI, and survival curves will be provided. Based on the KM estimates, the probabilities of experiencing the resolution and associated 95% CIs on Days 15 and 29 will be reported; in addition, the 25%, 50% (median), and 75% percentiles of the time to resolution with associated 95% CIs will be provided, as data permit. The survival rates between treatment groups will be compared using Log-rank test. The p-value from Log-rank test will be presented.

In addition, the time to the first occurrence of improvement of symptoms defined as the time from the initial symptom score of ≥ 1 to a reduction of ≥ 1 point on initial symptom score will also be evaluated for each individual symptom and the respiratory symptoms (cough, shortness of breath and difficulty breathing), using the KM method described above for the analysis of time to resolution of symptoms.

If a subject had a symptom score of 0 from Baseline through Day 29, then that subject will be excluded from the analysis.

Time to Improvement of Symptoms (days) = (Date of the first reduction of ≥ 1 point on initial symptom score of ≥ 1) - (Date of the initial symptom score of ≥ 1 at or after Baseline) + 1

A radar plot will be created by presenting each symptom score at each time point by treatment group.

SARS-CoV-2 Test

The SARS-CoV-2 tests will be performed at the end of the study or early discontinuation visit.

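### The fever score is due on Day 29 but the temperature it is scored from is not scheduled there, so scheduled fever information stops at the Day 15 visit

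*Protocol*

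**What the plan says.** Protocol 8.2 defines a four-item symptom score. Cough, breathing difficulty and muscle aches or fatigue are graded 0-3 by description. Fever is graded 0-4 by temperature band, and the source is named: "Fever will be scored based on temperature recorded as part of vital signs". Protocol 8.3 places temperature within the vital signs ("Vital signs will include body temperature, blood pressure, heart rate, and respiratory rate"), and footnote d of Table 1 says the same.

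In Table 1 the symptom-score row carries six marks, the last at Day 29 ("Symptom Score X X X X X X"). The vital-signs row carries five, the last at Day 15 ("Vital signs ^d X X X X X"). SAP Appendix A repeats both rows. The Day 29 list in Protocol 7.15 contains "SARS- CoV-2 infection symptom score" but neither vital signs nor a temperature.

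SAP 6.2 tabulates every symptom at every visit by arm, draws a radar plot of each symptom at each time point, and estimates time to resolution and time to improvement for each symptom separately. For resolution, "the probabilities of experiencing the resolution and associated 95% CIs on Days 15 and 29 will be reported"; improvement uses the same method. SAP 4.4 censors unresolved subjects at their last non-missing symptom assessment up to Day 29 and imputes no missing scores.

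**The concern.** Fever is the only symptom item that needs an instrument reading, and Day 29 is the only visit where the score is required without that reading. A site that follows the protocol literally must leave fever blank, score it without the reading that 8.2 prescribes, or take a temperature that the schedule does not request. Sites may choose differently.

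At stake are the fever results of one secondary endpoint: the Day 29 fever tabulation and radar-plot point, and whatever the Day 29 resolution and improvement probabilities are meant to add to those at Day 15.

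**Working it through.** The plan states no figure for this point, so there is none to reproduce. The check sets the schedule against the definition and then follows the consequence through the SAP's time-to-event formula.

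**Schedule (Protocol Table 1, repeated in SAP Appendix A)**

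| Visit | Symptom score due | Vital signs due |
|---|---|---|
| Screening | yes | yes |
| Day 1 | yes | yes |
| Days 3, 6 | yes | yes |
| Day 10 | yes | yes |
| Day 15 | yes | yes |
| Day 29 | yes | no |

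The text confirms that the empty cell is not an extraction fault. Sections 7.12 and 7.13 list both items for Days 10 and 15; Section 7.15 lists only the symptom score. The early-withdrawal visit in Section 7.14 includes vital signs, but applies only when participation ends before Day 15 is completed, so it cannot supply a Day 29 temperature. The gap is 1 of 4 items at 1 of 5 post-baseline visits (Days 3, 6, 10, 15, 29).

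**Latest scheduled temperature.** The window for the Day 15 visit is "Assessments should occur within +1 day of target Study Day", so Day 16 at the latest.

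**Longest observable time to fever resolution.** SAP 6.2 uses (date of first 0) − (date of initial score ≥ 1) + 1, and there is no Day 0.

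- Fever first scored on Day 1, resolved at the Day 15 visit held on Day 16: 16 − 1 + 1 = 16 days.
- Fever first scored on Day −2 (if that is the baseline value), same end: Day −2 to Day 16 spans 17 calendar days, so 17 + 1 = 18 days.
- With a temperature on Day 29 and fever first scored on Day 1: 29 − 1 + 1 = 29 days.

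Without a Day 29 temperature, no resolution can be recorded beyond 16 to 18 days, and the curve is flat from there to Day 29.

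**Illustration of size.** Assume 20 febrile subjects in an arm, none lost before the Day 15 visit, and k still febrile at that visit. The Kaplan-Meier resolution probability after that visit is then 1 − k/20.

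| k | Day 29 value, no Day 29 temperature | Day 29 value, temperature taken on Day 29 | Possible gap |
|---|---|---|---|
| 0 | 100% | 100% | 0 points |
| 1 | 95% | 95% to 100% | 5 points |
| 2 | 90% | 90% to 100% | 10 points |
| 4 | 80% | 80% to 100% | 20 points |

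The lower end applies if none of the k resolve, the upper end if all do. The 20 and the values of k are assumptions. For improvement, read k as the number whose fever score has not yet fallen by a point.

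**What does not depend on temperature.** The Ordinal Scale (primary endpoint), the other three symptoms, and the respiratory symptom score, which SAP 6.2 builds from cough and breathing difficulty alone.

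**The case against.** The strongest reply is that the protocol can be read as self-completing. Section 7.15 asks for the whole symptom score on Day 29 and 8.2 says fever comes from a temperature, so a careful site would take one; subjects are already there for a swab. This stands in part. A reader might infer that fever will be missing on Day 29 in every subject, but the documents do not support that: it predicts site behaviour, and the case report form is not available. What they do show is that the measurement is not scheduled, which leaves the choice to each site.

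A reader might also infer that the Day 29 fever-resolution estimate has no data behind it. That is wrong. The Kaplan-Meier probability is cumulative and uses the fever scores at Days 3, 6, 10 and 15. It lacks only later information.

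Nor must the two reported probabilities be identical. A subject febrile from Day 1 and first afebrile at a Day 15 visit held on Day 16 has a time of 16 days, which counts in the Day 29 figure but not in the Day 15 figure. The exact statement is that the Day 29 figure equals the curve's value after the Day 15 visit.

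The censoring date is open too. Because the other symptoms are scored on Day 29, the SAP 4.4 rule could place censoring for fever there rather than at the last fever score. The curve is flat under either reading; only the number shown at risk changes.

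Finally, the reach is small: one item of a secondary endpoint, in a study whose SAP calls it exploratory. That is accepted.

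**Conclusion.** The inconsistency holds and is minor. Fever is required on Day 29, its only defined source is not scheduled there, and Table 1, Section 7.15 and SAP Appendix A agree on the omission. Followed as written, the Day 29 fever summary and radar-plot point have no scheduled source measurement, and the fever resolution and improvement probabilities at Day 29 are the Day 15-visit values carried flat.

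The numerical effect depends on how many subjects are still febrile at the Day 15 visit. The documents do not give this number, so the 0 to 20 percentage points above are only an illustration. If every fever has resolved by then, the Kaplan-Meier figures are unaffected and only the Day 29 tabulation and plot remain without a source. The conclusion rests on sites doing what is scheduled and no more; any temperature taken on Day 29 without being scheduled would narrow the gap.

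**What to change.** Add body temperature, or the whole vital-signs row, to Day 29 in Protocol Table 1, Protocol 7.15 and SAP Appendix A. The cost is one temperature reading at an existing visit, plus matching edits in three places.

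If Day 29 visits have already taken place and no temperature was recorded, state in SAP 6.2 that fever is summarised only through the Day 15 visit, and that subjects still febrile are censored at their last fever score based on a temperature. Keep any Day 29 temperatures that were recorded; the restriction should not discard valid readings.

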8.3. Physical Examination and Vital Signs

A qualified medical person will perform a physical examination at all indicated visits.

- Physical examination: general appearance, head, eyes, ears, nose, throat, neck, cardiovascular, lungs, abdomen, lymph nodes, extremities, neurological, skin, musculoskeletal, and other.
- Vital signs will include body temperature, blood pressure, heart rate, and respiratory rate.

8.4. SARS-CoV-2 Testing

All testing associated with the conduct of the study will be conducted at a central laboratory designated by the Sponsor. At every sampling time point, a nasopharyngeal swab or an oropharyngeal swab will be taken. Directions for specimen collection, handling and transport will be provided in a Laboratory Manual.

8.5. Spirometry

American Thoracic Society or British Thoracic Society guidelines should be followed in the conduct of spirometry assessments performed at screening.

9. DESCRIPTION OF STUDY TREATMENT

9.1. Placebo

Sterile saline for inhalation will be used as the placebo.

9.2. PUL-042 Inhalation Solution

Additional information concerning PUL-042 including receipt, storage, preparation, and time windows for preparation and subject administration will be provided in the Pharmacy Manual.

The teratogenic effects of PUL-042 are unknown.

9.2.1. PUL-042

The investigational product, PUL-042 Inhalation Solution, is a combination of Pam2CSK4 acetate and ODN M362 sodium (4:1 molar ratio [Pam2:ODN]). PUL-042 is formulated as a solution in SWFI, USP, with no other excipients, at a pH of 5 to 8. Pam2 is a synthetic 6-amino acid lipopeptide, and ODN is a synthetic 25-base, single-stranded phosphorothioate oligodeoxynucleotide. The structure of Pam2 and the nucleotide sequence of ODN are shown in Section 5.2 (Figure 3).

The investigational product components (Pam2CSK4 and ODN M362 sodium) are manufactured by: Albany Molecular Research (Glasgow) Ltd. [name].

9.3. Packaging and Labeling

PUL-042 will be packaged as separate component solutions of Pam2 and ODN in 5-mL Type I sterile glass vials or 2-mL Type I sterile glass vials, sealed with a rubber injection stopper and an aluminum tear-off overseal. PUL-042 components will be manufactured, labeled, and packaged under Good Manufacturing Practice guidelines. Sterile saline for inhalation will be supplied by the investigative site.

9.4. Shipment and Storage

Individual components of PUL-042, Pam2 Solution and ODN Solution, are stored frozen (-20 ±5°C) at the drug distribution center and will be shipped to the site on dry ice.

Cartons containing 5-mL or 2-mL glass vials of individual PUL-042 components (Pam2 and ODN) will be sent to the clinical study site pharmacy. The study drug components will be stored frozen (-20 ±5°C) at the study site until ready for use.

9.5. Preparation and Administration

The pharmacist at the clinical site will be responsible for the preparation of the appropriate concentration of PUL-042 by dilution of the components of PUL-042 in SWFI. Specific instructions will be provided for the preparation of PUL-042 Inhalation Solution in the Pharmacy Manual. PUL-042 Inhalation Solution must be administered within 4 hours of preparation.

10. CONCOMITANT MEDICATIONS, TREATMENTS, AND PROCEDURES

All concomitant medications, including prescription and nonprescription over-the-counter drugs, vitamins, or nutritional supplements, taken during the 14 days prior to screening or while a participant is on study will be recorded in the electronic case report form (eCRF). Documentation will include start and stop dates and reasons for use.

Any diagnostic, therapeutic, or surgical procedures performed during the study period will be documented.

11. STUDY WITHDRAWAL

11.1. Study Termination

The entire study may be terminated at any point based on the evaluation of the study or development program by Pulmotect. A Data Safety Monitoring Board (DSMB) will review unblinded data on the first 20 subjects then again at 40 subjects and 60 subjects with additional ad hoc reviews at the request of the DSMB. The DSMB can also request that study enrollment be paused at any time should enrollment be faster than anticipated such that adequate safety review is not able to occur between the specified review meetings.

11.2. Subject Withdrawal/Lost to Follow-up

Subjects who are discontinued from dosing during the study and have received at least one dose of investigational treatment must be followed up to Day 29 according to the schedule of events specified above for pre-dose assessments. There will be no post-dose assessments for these subjects.

Subjects will be free to withdraw from the study at any time without giving a reason. Subjects will be considered withdrawn from the study in the event of any of the following reasons:

- Withdrawal of the subject's consent for any reason.
- Subject lost to follow-up prior to the Study Day 29 assessments.

In the event a subject withdraws from the study for any reason, the Investigator must notify Pulmotect as soon as possible and complete the applicable eCRF pages. An effort should be made to capture the reason(s) for withdrawal.

Subjects that withdraw should complete the Early Termination assessments as soon as possible.

A subject is considered lost to follow-up after 3 documented attempts to contact the subject without success.

Subjects who withdraw after the start of study drug administration will not be replaced.

